4.1 Outcomes

Primary Outcome:

The primary outcome is rate of change in cone spacing and rate of change in cone density as determined using AOSLO images of regions of interest (ROIs) preselected at baseline in eyes treated with CNTF compared to contralateral eyes treated with sham surgery over 30 months. Cone spacing and density will be measured by 3 independent graders who will remain fully masked to the treatment assignment throughout the duration of the trial. We will compare rates of change in cone spacing and cone density between CNTF-treated and contralateral sham-treated eyes through 30-months using pooled linear regression.

Secondary Outcomes:

Secondary outcome measures will involve comparing rates of change in standardized measures of visual function between CNTF- and sham-treated eyes. Secondary outcomes will include the following functional and structural assessments: mean and median change in best spectacle-corrected visual acuity (BCVA) using the ETDRS protocol, changes in visual field sensitivity and foveal sensitivity in decibels (dB) using automated static perimetry using the Humphrey visual field 10-2 protocol and rod and cone-mediated fundus-guided microperimetry using a modified Nidek MP1, changes in thickness of the outer nuclear layer (ONL) and outer segment plus RPE (OS+) layer thickness as measured using spectral-domain optical coherence tomography (SD-OCT), and changes in full-field ERG scotopic and photopic standard a- and b-wave amplitudes and timing from baseline to 36 months. All parameters except full-field ERG will be measured at 6, 12, 18, 24, 30 and 36 months after implant surgery; standard full-field ERG will be performed according to ISCEV standards at baseline, 12, and 24 months.

Safety Outcomes:

Safety of the NT-501 ECT technology implant has been demonstrated in prior Phase 1 and Phase 2 trials of the implant. Separately from efficacy outcomes which demonstrate a reduction or increase in function, safety parameters will continue to be collected and assessed by the following outcomes (occurrence of these outcomes does not necessarily require explant):

- Rejection or extrusion of the NT-501 device.
- Protocol-related abnormal findings from serum chemistry, hematology, and urinalysis (those abnormal findings that are determined to be clinically significant by the Principal Investigator).
- Peri-implant fibrosis, which either blocks the visual axis of the implanted eye or affects the lens or retina (minor/moderate fibrosis around the implant and/or the attachment point is an expected possibility and will be considered safe on ocular function). Attention should focus on fibrosis that may detach the retina.
- Development of choroidal neovascularization (CNV) in the implanted eye, in which case it may be considered a safety event and explant will be considered.

- Adverse events affecting ocular function, which are different from those expected in the normal course of RP or Usher Syndrome, which are thought to be potentially related to the implant.
- Local or systemic toxicities considered serious adverse events that are potentially related to the implant.

There are risks associated with the surgeries to implant and explant the device and with the sham surgery. In general, the risks of intra-ocular surgery are very small. Some side effects could occur locally in the eye and could affect the participant's vision. There may be pain or infection, a small amount of bleeding, cataract, vitritis, and/or mild astigmatism. A retinal detachment could also possibly occur. Participants may experience a transient red eye from superficial bleeding and itching or a foreign body sensation in the corner of the eye from irritation of the suture itself. These side effects are usually temporary and generally clear up in two weeks or less. In many cases, topical antibiotics and topical steroids can treat minor degrees of inflammation or infection. More serious infection or inflammation may require further surgery on the eye, likely with removal of the implant.

In addition, all adverse events will be collected regardless of severity or potential relationship to the implant, CNTF, or surgical procedure.

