6.4 Sample Size Rationale

The primary analysis will compare the mean rate of change in cone spacing and cone density between CNTF-treated and control eyes over the 24-month study period using pooled linear regression. With a minimum 10 patients the sample size will provide in excess of 80% power to detect a difference of 0.084 arcminutes in cone spacing (twice the effect reported per year in preliminary studies (Talcott et al, 2010), assuming a within-region standard deviation of 0.11 (based on preliminary data, and using a paired-subjects t-test as a basis for power calculations).

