3.1.5 Sample size calculation methodology

We used a simplified version of the analysis we plan in order to estimate the power for the more complex analysis. This reduces the analysis to a paired T-test. More specifically, we determined the rate of change over time of the cone spacing in our pilot patients, and computed a pooled standard deviation over all these regions (in untreated persons) from which we derived an expected standard deviation of the difference in the total change in cone spacing after two years of approximately 0.11. Using the standard formula for the sample size of a one-sample T-test

(e.g. Chow et al, 2007, formula 3.1.2), we find we would need a total of 17 individuals per group, or 20 adjusting for loss to follow-up.

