7.5.1.1 Primary analysis

While we consider both cone spacing and density to be primary outcome measures, for the purpose of formal hypothesis testing for the efficacy aims of the trial, we chose the outcome variable to be cone spacing. We will analyze cone spacing as the primary prespecified outcome, but also conduct an analogous analysis of cone density. Cone spacing as well as cone density will be measured longitudinally in regions of interest *selected prior to randomization and surgery* and followed over time. Specifically, as detailed in the flow sheet of examination procedures in the Protocol, we will consider acquiring measurements at the following times:

Baseline 1, within 7 weeks of implant surgery

Baseline 2, within 4 weeks of baseline 1

Six months (plus or minus 7 days)

Twelve months (plus or minus 14 days)

Eighteen months (plus or minus 14 days)

Twenty-four months (plus or minus 14 days)

Thirty months (plus or minus 14 days)

Thirty-six months (plus or minus 14 days)—this measurement is the primary outcome and is required

A minimum of seven regions of interest per eye will ideally be established from the Baseline 1 images. These specific regions will be followed longitudinally. Note that if outcome data were not available at a specific visit due to inability to acquire images from patients, the study could

optionally be continued at the discretion of the DSMC. Such decisions would be made independent (masked to) all outcome data.

The primary hypothesis test uses the 36-month observations.

We use the following notation. The data are hierarchical, with region nested within eye and eye nested within person. Let each region within each eye be labeled k , $k=1, \dots, n_{ij}$, where n_{ij} is the number of regions of interest identified within eye j of person i . We denote the control eye by $j=0$, and the treatment eye by $j=1$. We denote the study time by ℓ , with $\ell=0$ representing baseline, and $\ell=1$ representing the final followup. We let $Y_{ijk\ell mg}$ denote the outcome variable for person i , eye j , region k , time ℓ , repetition m , and grader g . In the case of the baseline visit, $m=1, 2$; for the followup, $m=1$; grader $g=1, 2$ identifies the two graders. We denote the foveal distance of each region of interest as D_{ijk} ; each region of interest is prospectively identified and followed over time, and these distances are therefore constant over time.

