Z scores will be used as the prespecified outcome variable, based on analysis of normal subjects. Spacing is determined by analysis of images, by two independent graders.

The baseline score for a region of interest for each grader is $(Y_{ijk01g} + Y_{ijk02g})/2$. The change score for each region of interest for grader g is $\Delta_{ijkg} = Y_{ijk\ell 1g} - (Y_{ijk01g} + Y_{ijk02g})/2$. The mean change score (averaging over graders) is $\Delta_{ijk} = (\Delta_{ijk1} + \Delta_{ijk2})/2$. The average change score for each eye is $\Delta_{ij} = (\sum_k \Delta_{ijk})/n_{ij}$. The difference between the treatment and control eyes for person i is $U_i = \Delta_{i1} - \Delta_{i0}$.

Under the null hypothesis, the differences U in change between treatment and control should have mean 0. We test this hypothesis using the Wilcoxon rank sum test.

Additional analyses may be reported. In each case, we will distinguish between such supplementary analyses and the primary analysis.

- The grader-specific difference in change scores, analyzed using Rosner's clustered version of the Wilcoxon rank sum test
- Analyses of covariance, in which the baseline is used as a regressor and the outcome variable is the final value. These models will be at the level of the individual ROI, clustering on eye and person.
- Subset analyses in which the analysis is restricted to regions of interest in which both graders' results are available at all visits. Note that this does not eliminate bias, since missingness of follow-up data occur post-randomization.

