7.5.1.3 Longitudinal analysis

As a complement to the above analysis, we will also model the clinical trial data using linear mixed models (e.g. Yasui et al, 2004), a modeling approach we have used in analysis of cone spacing and density data in the pilot study (Talcott et al., 2011)—provided interim observations are available.

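### Protocol 4.1 and 6.4 name an undefined pooled linear regression for the primary rate comparison; read literally it does not hold its 5% error rate, and it conflicts with the SAP's participant-level primary test.

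*Protocol*

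**What the plan says.** Protocol 4.1 gives one method for the primary outcome: "We will compare rates of change in cone spacing and cone density between CNTF-treated and contralateral sham-treated eyes through 30-months using pooled linear regression". Protocol 6.4 repeats it over a different period: "between CNTF-treated and control eyes over the 24-month study period using pooled linear regression". Neither section writes out the model or says how repeated ROIs, eyes or persons enter it. Protocol 6.1 randomises one eye per participant to the implant, and 4.7 requires at least 7 ROIs in each eye. Protocol 6.4 takes its power from a paired t-test, and 6.5 leaves the detailed analysis to a SAP.

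SAP 7.5.1.1 takes another route. It says: "The data are hierarchical, with region nested within eye and eye nested within person". It averages z-score changes over graders and ROIs to one value per eye, forms one treated-minus-control difference per person, and applies a Wilcoxon test at month 36. The rate of change appears only in SAP 7.5.1.3: "As a complement to the above analysis, we will also model the clinical trial data using linear mixed models". That model depends on interim observations being available, and its random effects are not listed.

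**The concern.** The eye is the randomised unit and eyes are paired within a person. The treatment contrast should therefore be judged against how much the two eyes of one person differ in progression when the implant does nothing. A single regression over all ROI-by-visit values, with independent errors and one slope per arm, does not do this. It charges no eye-level or ROI-level slope variation to the contrast, which makes its standard error too small. It also leaves fixed level differences between ROIs in the residual, which makes its standard error too large. The two faults pull in opposite directions, and nothing makes them cancel.

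The rate of change is the outcome in the trial's title. If it were reported by that method, the p-value and confidence interval would not answer the treatment question, and the paired-test power in Protocol 6.4 would belong to a different analysis.

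**Working it through.** **1. The plan's own power figures.** Inputs: difference 0.084 arcmin over two years (Protocol 6.4, SAP 3.1.2); SD 0.11, described in SAP 3.1.5 as the "standard deviation of the difference in the total change in cone spacing after two years of approximately 0.11"; two-sided alpha 0.05; paired (one-sample) t-test. The noncentrality is (0.084/0.11)√n = 0.7636√n.

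- SAP: the normal formula gives (1.960 + 0.842)² × 0.11²/0.084² = 13.5, so 14. The exact t calculation needs 16 (81.4%). The SAP's 17 gives 84.0%, and 17/0.85 = 20. The SAP figure is reproduced to within one participant.
- Protocol: n = 10 gives noncentrality 2.415 on 9 df and power 57.7%, against a stated figure above 80%. It is not reproduced. For comparison, n = 20 gives 89.9% and n = 30 gives 98.1%.
- The Protocol figure can be reached if 0.11 is an SD per ROI, as 6.4's within-region label may suggest. The participant-level SD is then 0.11√((1+6ρ)/7), where ρ is the correlation between ROIs of the same participant. Power at n = 10 is 94.8% for ρ = 0.25, 81.1% for 0.5, 68.0% for 0.75 and 57.7% for 1. So ρ must be about 0.5 or less.

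**2. Error rate of the literal pooled regression.**

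From the documents: N = 20 (SAP 3.1.5), R = 7 ROIs per eye, D = 0.11, two baselines and months 6 to 30. Assumed, because the documents do not give them: residual SD 0.05; SD s of ROI levels from 0 to 0.3 arcmin; whether slope variance lies between eyes or between ROIs. Slope variation shared by both eyes is left out: it cancels in the contrast and only adds to the residual.

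In two-year units the times are 0, 0, 0.25, 0.5, 0.75, 1, 1.25. The sum of squares about the mean is S = 1.4286, the mean of t² is 0.491, and N·R·S = 20 × 7 × 1.4286 = 200 per arm. Slope variance per ROI is 0.11²/2 = 0.00605.

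- Variance reported by the regression: 2(s² + 0.00605 × 0.491 + 0.05²)/200 = (s² + 0.00547)/100.
- True variance, slopes varying between eyes: 0.11²/20 + 2 × 0.0025/200 = 0.000630 (SE 0.0251).
- True variance, slopes varying between ROIs only: 0.11²/140 + 0.000025 = 0.000111 (SE 0.0106).
- Null rejection rate: 2[1 − Φ(1.96 × reported SE/true SE)].

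| s (arcmin) | Reported SE | Eye level: SE ratio | Rejects (simulated) | ROI level: SE ratio | Rejects (simulated) |
|---|---|---|---|---|---|
| 0 | 0.0074 | 0.29 | 56% (57-58%) | 0.70 | 17% (17-18%) |
| 0.1 | 0.0124 | 0.50 | 33% (30-34%) | 1.18 | 2% (2%) |
| 0.15 | 0.0167 | 0.67 | 19% (19%) | 1.58 | 0.2% (0.2-0.4%) |
| 0.3 | 0.0309 | 1.23 | 1.6% (1-2%) | 2.93 | 0% (0%) |

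The simulated figures come from repeated Monte Carlo runs of the same model. In those runs a one-sample t-test on each participant's difference in mean per-eye slope rejected in 4-6%. Both variances scale as 1/N, so the ratio does not depend on N: simulated rejection at s = 0 with eye-level slopes was 55% at both n = 10 and n = 30.

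**3. Power in the other direction.** At n = 10 and s = 0.3, simulated power for 0.084 arcmin is 46-50% with the pooled regression. With the paired slope test it is about 58% if slope variance is all at eye level, and above 99% if it is all at ROI level.

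**The case against.** The strongest reply is that the operative plan does not use this method. Protocol 6.5 hands the analysis to the SAP, and SAP 7.5.1.1 works with one value per participant ("The difference between the treatment and control eyes for person i is" a single number). The SAP's optional ROI-level covariance analysis clusters on eye and person, its longitudinal analysis is a mixed model, and it nowhere mentions pooled regression. That stands. A reader might infer that the trial's primary p-value is invalid; the documents do not support this.

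Second, the Protocol never defines the regression. Independence of all ROI values and one common slope per arm are the literal reading, not stated assumptions. That also stands, but an undefined primary method is itself a reason to amend the text.

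Third, the 0.11 is pooled over regions in SAP 3.1.5 and called within-region in Protocol 6.4, so it need not be true eye-level variation. That is why both allocations are shown. The ROI-level results are much milder at low spread and conservative at high spread.

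Fourth, a reader might infer that the pooled method generally produces false positives, or generally halves the power. Neither follows. ROIs lie at different distances from the fovea, so zero spread in level is unlikely in arcmin. The SAP's z-scores would reduce the spread by an unknown amount. With eye-level variance at SD 0.11 and n = 10, the power loss at s = 0.3 is only about 9 or 10 points.

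**Conclusion.** The point holds as a conflict between Protocol and SAP on the primary method, together with a Protocol method that, read literally, lacks a valid error rate. At n = 20 its null rejection lies between about 57% and 0% over the ranges shown. It comes near 5% only by coincidence of variance components, and more participants do not help. Direction and size rest on an assumed residual SD of 0.05, an assumed ROI-level spread, and an allocation of slope variance that the documents do not settle. The SAP's primary test is not touched by this.

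The related power statement in Protocol 6.4 fails as written if 0.11 is the participant-level SD, as the SAP's own sample size calculation takes it to be. The same inputs lead the SAP to 17 participants and the Protocol to 10. This should be corrected, but it does not undermine the SAP's planned primary inference.

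**What to change.** In Protocol 4.1 and 6.4, replace the pooled regression with a participant-level analysis: fit a slope over the scheduled visits for each ROI, average the slopes within each eye, take the implant-minus-sham difference for each participant, and test those differences with a two-sided paired test. A mixed model with random eye-level intercepts and slopes can be listed as supporting. It is not equivalent to the paired test, and a fuller version with random slopes at person, eye and ROI level may not be estimable with 10 to 30 participants.

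Changing the Protocol alone would leave it in conflict with the SAP. Amend SAP 7.5.1.1 at the same time so that both documents name one primary method, one form of outcome (slope or change score) and one time point out of 24, 30 and 36 months. If the sponsor prefers the SAP's change score, the Protocol should name that and list the slope test as secondary.

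In Protocol 6.4, restate the power for the chosen test and say whether 0.11 is per ROI or per participant. For the paired t-test at participant-level SD 0.11 the figures are about 58% at n = 10, 84% at n = 17 and 90% at n = 20.

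Cost: wording in both documents and no new data. The interval will be wider than the pooled one when eyes differ in progression rate, and the stated power at 10 participants becomes less favourable.

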4.2 Inclusion Criteria

1. Participant must be between 18 and 55 years of age.
2. Participant must have a diagnosis of retinitis pigmentosa or Usher syndrome type 2 or 3.
3. Participant must understand and sign the protocol informed consent. If the participant's vision is impaired to the point where he/she cannot read the informed consent document, the document will be read to the participant in its entirety.
4. Best-corrected visual acuity must be no worse than 20/63 (at least 59 letters).
5. Participants must have clear natural lenses.
6. Participants must have less than 6 diopters myopia.
7. Participants must be medically able to undergo ophthalmic surgery for the NT-501 device insertion and be able to undergo all assessments and tests associated with the protocol.

8. Females of childbearing potential (**women with last menses \leq 1 year prior to screening**) must agree to use an effective form of birth control from study onset until they complete the study.
9. Participants must have reproducible baseline AOSLO image montages at 2 baseline imaging sessions with quality suitable to identify a minimum of 7 regions of interest (ROIs) at which reliable cone spacing and/or density measures can be made over the central 5.7 degrees.
10. Participants must have interocular symmetry of disease severity as measured by cone spacing, with a difference of less than 2 standard deviations in average cone spacing z-scores at the selected ROIs between the 2 eyes.
11. Participant's clinical diagnosis must be consistent with retinal degeneration in the set of retinitis pigmentosa (RP) dystrophies characterized by the following features:
 - a) clinical evidence of progressive photoreceptor cell dysfunction and degeneration of the outer retina
 - b) intraretinal 'bone-spicule'-like pigment observed on clinical examination
 - c) peripheral visual field constriction documented on standard testing
 - d) symptomatic night blindness
 - e) reduction of both rod and cone electroretinogram (ERG) responses.

For purposes of this study, individuals diagnosed with Retinitis Pigmentosa or Usher Syndrome Type 2 or Type 3 (without profound deafness or cochlear implants) who meet the inclusion criteria will be considered as potential candidates for this study. A maximum of 4 Usher Syndrome Type 2 or Type 3 participants may be enrolled in this trial.

4.3 Exclusion Criteria

1. Participant is medically unable to comply with study procedures or follow-up visits.
2. Participant who has any of the following lens opacities: cortical opacity $>$ standard 3, posterior subcapsular opacity $>$ standard 3, or a nuclear opacity $>$ standard 3 as measured on the AREDS clinical lens grading system; or participant is pseudophakic or aphakic.
3. Participant has history of corneal opacification or lack of optical clarity.

4. Participant has undergone LASIK surgery or other refractive surgery for either eye.
5. Participant has nystagmus.
6. Participant has greater than 6 diopters myopia.
7. Participant has cystoid macular edema with cysts present within 4 degrees of the foveal center.
8. Participant has fewer than 7 ROIs present on 2 baseline AOSLO image montages.
9. Participant has retinal vascular disease such as diabetic retinopathy or prior retinal vascular occlusive disease.
10. Participant has chronic requirement (e.g., \geq 4 weeks at a time) for ocular medications or has disease(s) that in the judgment of the examining physician are vision threatening, toxic to the lens, retina, or optic nerve or may affect the primary outcome.
11. Participant has a requirement of acyclovir and/or related products during study duration. To be eligible for this study, the participant must discontinue use of these products prior to enrollment and must not continue with the products until after they have completed the study.
12. Participant is receiving systemic steroids or other immunosuppressive medications.
13. Participant is currently participating in or has participated in any other clinical trial of a drug by ocular or systemic administration within the last 6 months.
14. Participant has previous exposure to an intra-ocular device or implant into the eye (excluding intra-ocular lens).
15. Participant has uveitis or other retinal inflammatory disease.
16. Participant has a history of myocardial infarction within the last 12 months.
17. Participant is pregnant or lactating.
18. Participant is considered immunodeficient or has a known history of HIV. A laboratory test for HIV will be performed, and a positive result is also an exclusion criterion.
19. Participant with a history of ocular herpes zoster.
20. Participant is on chemotherapy.

21. Participant has a history of malignancy, except study participant with cancer treated successfully ≥ 5 years prior to inclusion in the trial.
22. Participant with severe hearing disabilities in both ears.
23. Participant who has been diagnosed and treated for amblyopia as an infant.
24. Participant who, in the opinion of the study doctor, will not be a good study subject.

[figure not shown]
